7.0 STUDY DESIGN AND PROCEDURES

This is a open label pilot study of abemaciclib administered orally to participants with recurrent, locally advanced, unresectable, or metastatic BTC. This study consists of a screening period of up to 28 days, up to eight 28-day treatment cycles, an EOT visit and follow-up visits every 3 months (\pm 7 days) 6 months after last dose of the study drug then every 6 months(\pm 7 days) thereafter until death .

The Principal Investigator will determine whether the participant meets all inclusion/exclusion criteria.

Each cycle will consist of 28 days of twice daily dosing of abemaciclib. Participants must receive a minimum of two 28 day cycles to be considered evaluable for the primary endpoint of ORR unless they withdraw earlier due to rapid disease progression. If a participant is deriving clinical benefit, he or she may receive additional cycles until one of the criteria for discontinuation is met.

Participants who are deriving clinical benefit after completing the treatment period may continue on additional cycles of therapy at the discretion of the sponsor and the medical monitor from the DSMC. Any participant that continues on abemaciclib after completing the treatment period will be monitored and assessed for tumor response per clinical routine per principal investigator.

Participants who complete treatment or who are withdrawn from treatment early will have an end of treatment visit. Participants with measurable disease who end treatment on a cycle at which a tumor response assessment is not planned should have end of treatment CT scans/MRI scans. Follow up visits will be performed every three months \pm 4 days 6 months for the subsequent anticancer therapy and survival then thereafter every 6 months (\pm 7 days) for survival only till death. It will be done by either clinic visit or phone call.

7.1 General Design/Phase/Schema

This is an open label pilot study to determine the efficacy and safety/tolerability of abemaciclib in participants with locally advanced, unresectable, or metastatic biliary tract cancer who have failed one or more lines of systemic therapy, or treatment-naïve subjects who either decline or being considered not a good candidate first-line systemic chemotherapy per the opinion of the treating physician 7.1.1 Enrollment/Randomization

This is a non-randomized study and thus participants will be enrolled sequentially. Participants will be screened for eligibility after signing the informed consent form.

7.1.2 Participant Population

Participants with histologically confirmed advance or metastatic biliary tract cancer including cholangiocarcinoma (intra-hepatic or extra-hepatic bile ducts), ampullary carcinoma, or gallbladder carcinoma who progressed following one or more lines of systemic therapy, will be enrolled if they meet eligibility criteria.

7.1.3 Number of sites/number of participants

This is a single center study that will be conducted at the Penn State Cancer Institute. In the future, additional study sites may be added if needed to assist with accrual numbers. Any addition of new sites and related modification to the protocol will be reviewed and approved in advance by the IRB and other applicable oversight bodies. Approximately up to 20 subjects may be enrolled to attain at least 10 evaluable participants.

7.1.4 Sample Size consideration

Refer to section 8.1.

7.1.5 Study Treatment

Abemaciclib will be given as a single oral agent. The starting dose will be 200 mg twice daily. One cycle = 28 days. There will be no protocol scheduled hiatus and daily dosing will be continuous unless there is unacceptable toxicity, disease progression, or death.

7.1.6 Dosing Adjustments, Delays and Discontinuation

Abemaciclib Dose Modification for Grade 3 or 4 AEs

| Dose Level | Abemaciclib Dose |
|---------------------------|--------------------|
| Recommended starting dose | 200 mg twice daily |
| First dose reduction | 150 mg twice daily |
| Second dose reduction | 100 mg twice daily |
| Third dose reduction | 50 mg twice daily |

Complete blood counts with differentials and complete metabolic panel will be monitored every 2 weeks for the first 2 months, then monthly for the next 2 months, at the beginning of every cycle.

7.1.7 Subject Evaluability and Subject Replacement

Approximately up to 20 subjects will be enrolled to attain at least 10 evaluable participants. Participants who voluntarily withdraw from the study for a reason other than tumor progression or inability to tolerate treatment may be replaced.

7.1.8 Safety Analysis

A safety analysis will be requested to review all safety data following the recruitment of 5 participants. The study may be terminated early if unexpected toxicities are observed. Following study termination, the internal PSCI DSMC will complete an expedited review of all efficacy and safety data; All regulatory bodies will be notified of study termination within no more than 2 business days of such a decision.

7.1.9 Safety Monitoring and Study Stopping Rules

In accordance with administrative, legal and ethical requirements documented in this protocol, safety monitoring will be performed by an internal Data Safety Monitoring Committee (DSMC). The DSMC of PSCI will review safety data per DSMC charter. The principal investigator (PI) will continuously monitor study progress for safety and will hold routine meetings with the study team and disease center personnel to review overall conduct and progress of this study. The frequency of such meetings will be dependent upon accrual to the trial and issues that arise. Study team meetings will include discussion of accrual, adverse events/safety issues, response and overall progress of the trial. Unexpected and related adverse events will be reported as they arise as well as any significant literature reporting developments that may affect the safety of participants in this study. Serious and unexpected adverse events will be reported to PSCI DMSC.

This study will be suspended or terminated prematurely for any of the following reasons:

- A death that is unexpected and at least probably related to abemaciclib
- Severe anaphylactic reaction to abemaciclib, either active ingredient, metabolites or excipients
- Any event, that, in the opinion of the Principal Investigator, or internal monitoring team, warrant immediate review by the PSCI DSMC
- Any other safety finding assessed as related to abemaciclib that, in the opinion of the PSCI DSMC, contraindicates further dosing of any participant.
- Any interim finding that, in the opinion of the Principal Investigator, suggests that the study has no clinical benefit for the participants.

7.1.10 Study Duration

- Enrollment period: 36 months
- Length of study: 48 months
- Anticipated length of study for each participant: 6 months

7.1.11 Study Drug

Abemaciclib will be stored in the limited access Penn State Health Investigational Drug Pharmacy. Maintenance, secure storage, and accountability of abemaciclib will be ensured according to institutional policies and procedures for investigational medications.

Abemaciclib is stored at room temperature. Refer to package label for specific storage conditions and instructions. Abemaciclib will be provided in 50 mg capsules in 60 count bottles. The Investigational pharmacist may dispense the medication directly to the research participant or the designated research team member.

7.2 Study Procedures and Assessments

Refer to Appendix B: Protocol Required Interventions and Assessments.

7.2.1 Procedures at Screening

A signed and dated informed consent form will be obtained before screening procedures commence. Evaluations obtained as part of routine medical care and performed during the screening period may be used for the protocol required evaluations.

After informed consent is obtained, participants who are screened will be assigned a unique identifier number such that all participants are given consecutive identification numbers in successive order.

A participant who is screened but not enrolled may be re-screened.

The following procedures and assessments will be performed within 28 days prior to C1D1 visit:

- Obtain histology report confirming diagnosis of malignancy
- Review inclusion/exclusion criteria
- Tumor evaluation through diagnostic imaging and RECIST v1.1 reading, including CT or MRI scans of chest, abdomen, and pelvis with contrast, and brain MRI, or PET CT scan
- Archival tumor samples will be collected for subjects for confirmation of diagnosis, as well as, for determination of exploratory mutational analysis.
- If no archival tumor samples are available, fresh biopsy will be collected for subjects for confirmation of diagnosis, as well as, for determination of exploratory mutational analysis.
- Review medical history (to include demographics, tobacco use (if smokes or smoked, and smoking pack year), surgical and psychiatric history and cancer treatment history)
- Review prior medication history (those medications taken within the last 28 days before the start of study treatment)
- Full physical examination including height, weight and vital signs measurements (temperature, heart rate, respiration rate and blood pressure).
- ECOG performance status
- Triplicate 12-lead ECG
- Clinical laboratory tests include hematology (complete blood counts with differential), serum chemistry (complete metabolic panel including Na, K, Cl, CO2, blood urea nitrogen, creatinine, glucose, aspartate aminotransferase, total bilirubin, alkaline phosphatase, alanine aminotransferase, albumin), coagulation profile including prothrombin time (PT), international normalized ratio (INR), partial thromboplastin time (PTT), CA 19-9, urinalysis)

The following procedures and assessments will be performed within 7 days prior to C1D1 visit:

Serum pregnancy test.

Participants who continue to meet all inclusion and exclusion criteria will be enrolled in the study.

7.2.2 Procedures During Study Drug Treatment

7.2.2.1 Procedures During Treatment Cycles (28-Day Cycles)

Study procedures and assessments will be performed as described below. No extra capsules of abemaciclib will be distribute to participants for each cycle.

The following procedures and assessments will be performed on C1D1 and C2D1:

- Physical examination, including weight and vital signs measurements.
- ECOG performance status
- AEs
- Concomitant medication
- 12-lead ECG (C1D1 and subsequent cycles if clinically indicated)
- Clinical laboratory tests
- EORTC-QLQ-C30 (see Appendix C)
- Dispense Abemaciclib
- Collect unused Abemaciclib (C2D1 only)
- Review participant drug diary and compliance with study medication (C2D1 only)
- Extracellular vesicle detection (C1D1 only)

The following procedures and assessments will be performed on C1D15 and C2D15:

- Physical examination, including vital signs measurements.
- ECOG performance status
- AEs
- Concomitant medication
- Clinical laboratory tests

The following procedures and assessments will be performed on C3-C8D1:

- Physical examination, including weight and vital signs measurements. Vital signs include temperature, heart rate, respiration rate and blood pressure.
- ECOG performance status
- AEs
- Concomitant medication
- Tumor evaluations every 8 weeks through diagnostic imaging and RECIST v1.1 reading, including CT or MRI of abdomen and pelvis with contrast every 8 weeks (± 7 days).
- Clinical laboratory tests
- EORTC-OLO-C30

- Dispense Abemaciclib
- Collect unused Abemaciclib
- Review participant drug diary and compliance with study medication
- Extracellular vesicle detection will be performed every 8 weeks (± 3 days) until objective disease progression or study completion.

7.2.3 Procedures During the End-of-Treatment Visit

For participants who complete the study or withdraw prematurely, final evaluations will be performed at the EOT visit or on the last day the participant receives the study drug.

Participants with ongoing AEs or clinically significant abnormal laboratory test results (as interpreted by the Principal Investigator) will be monitored per the Principal Investigator and AEs will be recorded and reported per protocol Section 10.1.2.

If a participant withdraws from the study during the treatment period, the reason must be determined and recorded on the participant's electronic case report form (eCRF). For participants who withdraw consent, every attempt will be made to determine the cause.

The following procedures will be performed at the EOT visit (up to 30 days \pm 7 days) from last dose of study drug), unless otherwise specified:

- Physical examination including body weight and vital sign measurements
- ECOG performance status
- AEs
- Concomitant medication
- Collect unused Abemaciclib
- Review participant drug diary and compliance with study medication
- Tumor evaluations through diagnostic imaging (CT/MRI/PET) every 8 weeks (± 3 days) until objective disease progression.
- Subsequent post-study treatment anti-cancer therapy
- Clinical laboratory tests
- 12-lead ECG if clinically indicated
- EORTC-QLQ-C30
- Extracellular vesicle detection will be performed every 8 weeks (± 3 days) until objective disease progression or study completion

7.2.4 Procedures at Follow-Up Visits

- Tumor evaluations: every 3 months (± 7 days) beginning 3 months after the last dose of study drug for subjects who have not progressed.
- Survival/death assessment, including data and cause of death if applicable. Every 3 months (± 7 days) x2, beginning 3 months after last dose of the study drug then every 6 months (± 7 days) thereafter. The assessment can be performed at standard of care visits or any other possibly treatments, or via phone calls.

• Subsequent post-study treatment anticancer therapy: every 3 months (± 7 days) x2, beginning 3 months after last dose of the study drug then every 6 months (± 7 days) thereafter.

7.2.5 Unscheduled Visits

An unscheduled visit may be performed at any time during the study at the request of the participant or as deemed necessary by the Principal Investigator. The date and reason for the unscheduled visit will be recorded on the CRF, as well as any other data obtained (e.g. AEs, concomitant medications and treatments, and results from procedures or tests).

7.3 Treatment of participants

7.3.1 Study Drugs Administered

The investigational drug, abemaciclib, will be administered as 50 mg capsules.

7.3.2 Study drug information

When used as monotherapy, the recommended dose of abemaciclib is 200 mg taken orally twice daily. Continue treatment until disease progression or unacceptable toxicity.

7.3.3 Packaging/Preparation/Dispensing/Storage

Abemaciclib 50 mg capsules are oval beige. Capsules are suppled in 60 count bottles. Drug is to be stored at room temperature.

7.3.4 Administration

Participant will be administered a 200 mg dose (i.e., four 50 mg capsules) of abemacilib orally twice daily. The participant will be instructed to swallow abemaciclib as a whole capsule and not to chew, crush or split capsules before swallowing. Participants should not ingest abemaciclib capsules if broken, cracked, or otherwise not intact. Doses should be taken at approximately the same time every day, twice daily. Capsules can be taken orally with or without food. If the participant vomits or misses a dose of abemaciclib, the participant will be instructed to take the next dose at its scheduled time.

Participants will also be provided with a diary and instructed to keep a twice daily record of the times they have taken their medications and any other events such as vomiting, diarrhea, etc.

7.3.5 Overdose

There is no known antidote for abemaciclib. The treatment of overdose of abemaciclib should consist of general supportive measures.

7.3.6 Missed doses

If a participant vomits or misses a dose, the participant will be instructed to take the next dose at its scheduled time.

7.3.7 Restriction on Concomitant Therapies

Effect of Other Drugs on Abemaciclib

Strong CYP3A Inhibitors

Strong CYP3A4 inhibitors increased the exposure of abemaciclib plus its active metabolites to a clinically meaningful extent and may lead to increased toxicity. all strong CYP3A inhibitors are excluded from use during this clinical trial. Patients should avoid grapefruit, orange juice, pomelo products.

Ketoconazole

Avoid concomitant use of the strong CYP3A4 inhibitor ketoconazole. Ketoconazole is predicted to increase the AUC of abemaciclib by up to 16-fold.

Itraconazole (a strong CYP3A inhibitor) is predicted to increase the relative potency adjusted unbound AUC of abemaciclib plus its active metabolites (M2, M18 and M20) by 2.2-fold. Co-administration of 500 mg twice daily doses of clarithromycin (a strong CYP3A inhibitor) with a single 50 mg dose of abemaciclib (0.3 times the approved recommended 150 mg dosage) increased the relative potency adjusted unbound AUC0-INF of abemaciclib plus its active metabolites (M2, M18, and M20) by 1.7-fold relative to abemaciclib alone in cancer patients.

Moderate CYP3A Inhibitors: Diltiazem and verapamil (moderate CYP3A inhibitors) are predicted to increase the relative potency adjusted unbound AUC of abemaciclib plus its active metabolites (M2, M18, and M20) by 1.7-fold and 1.3-fold, respectively.

Strong CYP3A Inducers

Co-administration of 600 mg daily doses of rifampin (a strong CYP3A inducer) with a single 200 mg dose of abemaciclib decreased the relative potency adjusted unbound AUC_{0-INF} of abemaciclib plus its active metabolites (M2, M18, and M20) by 67% in healthy subjects.

Moderate CYP3A Inducers: The effect of moderate CYP3A inducers on the pharmacokinetics of abemaciclib is unknown.

Loperamide: Co-administration of a single 8-mg dose of loperamide with a single 400-mg dose of abemaciclib in healthy subjects increased the relative potency adjusted unbound AUC_{0-INF} of abemaciclib plus its active metabolites (M2 and M20) by 12%, which is not considered clinically relevant.

Fulvestrant: In clinical studies in patients with breast cancer, fulvestrant had no clinically relevant effect on the pharmacokinetics of abemaciclib or its active metabolites.

Effects of Abemaciclib on Other Drugs

Loperamide: In a clinical drug interaction study in healthy subjects, co-administration of a single 8 mg dose of loperamide with a single 400 mg abemaciclib (2.7 times the approved recommended 150 mg dosage) increased loperamide AUC_{0-INF} by 9% and C_{max} by 35% relative to loperamide alone. These increases in loperamide exposure are not considered clinically relevant.

Metformin: In a clinical drug interaction study in healthy subjects, co-administration of a single 1000 mg dose of metformin, a clinically relevant substrate of renal OCT2, MATE1, and MATE2-K

transporters, with a single 400 mg dose of abemaciclib (2.7 times the approved recommended 150 mg dosage) increased metformin AUC_{0-INF} by 37% and C_{max} by 22% relative to metformin alone. Abemaciclib reduced the renal clearance and renal secretion of metformin by 45% and 62%, respectively, relative to metformin alone, without any effect on glomerular filtration rate (GFR) as measured by iohexol clearance and serum cystatin C.

Fulvestrant: In clinical studies in patients with breast cancer, abemaciclib had no clinically relevant effect on fulvestrant pharmacokinetics.

In Vitro Studies

Transporter Systems: Abemaciclib and its major active metabolites inhibit the renal transporters OCT2, MATE1, and MATE2-K at concentrations achievable at the approved recommended dosage. The observed serum creatinine increase in clinical studies with abemaciclib is likely due to inhibition of tubular secretion of creatinine via OCT2, MATE1, and MATE2-K [see Adverse Effects (7.1)]. Abemaciclib and its major metabolites at clinically relevant concentrations do not inhibit the hepatic uptake transporters OCT1, OATP1B1, and OATP1B3 or the renal uptake transporters OAT1 and OAT3.

Abemaciclib is a substrate of P-gp and BCRP. Abemaciclib and its major active metabolites, M2 and M20, are not substrates of hepatic uptake transporters OCT1, organic anion transporting polypeptide 1B1 (OATP1B1), or OATP1B3.

Abemaciclib inhibits P-glycoprotein (P-gp) and BCRP. The clinical consequences of this finding on sensitive P-gp and BCRP substrates are unknown.

CYP Metabolic Pathways: Abemaciclib and its major active metabolites, M2 and M20, do not induce CYP1A2, CYP2B6, or CYP3A at clinically relevant concentrations. Abemaciclib and its major active metabolites, M2 and M20, down regulate mRNA of CYPs, including CYP1A2, CYP2B6, CYP2C8, CYP2C9, CYP2D6 and CYP3A4. The mechanism of this down regulation and its clinical relevance are not understood. However, abemaciclib is a substrate of CYP3A4, and time-dependent changes in pharmacokinetics of abemaciclib as a result of autoinhibition of its metabolism was not observed.

P-gp and BCRP Inhibitors: In vitro, abemaciclib is a substrate of P-gp and BCRP. The effect of P-gp or BCRP inhibitors on the pharmacokinetics of abemaciclib has not been studied.

Thus, all strong CYP3A inhibitors are excluded from use during this clinical trial. Patients should avoid grapefruit, orange juice, pomelo products.

Strong CYP3A Inducers

Coadministration of abemaciclib with rifampin, a strong CYP3A inducer, decreased the plasma concentrations of abemaciclib plus its active metabolites and may lead to reduced activity. For the purpose of this study, all CYP3A inducers will not be permitted on this study; please see Appendix A and refer to crediblemeds.org for a more comprehensive list of prohibited medications.

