3.4 Early Withdrawal /Discontinuation of the Study Treatment

A participant will be withdrawn from study treatment for any of the following reasons:

- Withdrawal of consent from the study by the participant at any time and for any reason. The reason for elective withdrawal will be documented in the research record if known.
- Unacceptable toxicity in the judgement of the Principal Investigator.
- Toxicity possibly related to abemaciclib does not resolve in14 days.
- Progression of disease requiring alternative systemic treatment.
- Significant participant or protocol noncompliance that, in the opinion of the Principal Investigator, warrants withdrawal of treatment. For example, participant is noncompliant in taking prescribed study medication or fail to return for scheduled follow up visits.
- Development of intercurrent, non-cancer related illnesses or complications that prevent either continuation of therapy or regular follow up.
- In the opinion of the Principal Investigator, it is inappropriate for the participant to continue on the study.
- Best medical interest of the participant at the discretion of the Principal Investigator.
- Subject becomes pregnant.
- Participant become lost to follow up. Participants who are unable to be located despite 3 documented attempts at contact (telephone, mail, or email) followed by a certified letter will be considered lost to follow up and rendered off study.
- Premature study closure.

Every effort should be done to help assure participants who are withdrawn from study treatment undergo the planned end of study follow up, end of treatment follow-up as outlined.3.4.1 Follow-up

An EOT visit will occur 30 ± 7 days from the last study treatment. Follow-up visits will occur every 3 months (\pm /- 7 days) x2, beginning 3 months after last dose of the study drug, then every 6 months (\pm 7 days) thereafter.

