7.4.5 General Guidance for Interstitial lung disease (ILD)/Pneumonitis events

Interstitial lung disease (ILD) / pneumonitis has been identified as an adverse drug reaction for abemaciclib. Adverse events reported included events such as interstitial lung disease, pneumonitis, obliterative bronchiolitis, organizing pneumonia, pulmonary fibrosis. The majority of events were Grade 1 or Grade 2 with serious cases and fatal events reported.

Monitor for clinical symptoms or radiological changes indicative of ILD/pneumonitis and please ask patients to report any new or worsening pulmonary symptoms. Symptoms may include hypoxia, cough, dyspnea, or interstitial infiltrates on radiologic exams.; these symptoms should be investigated and treated as per local clinical practice and/or guidelines (including corticosteroids as appropriate). Infectious, neoplastic, and other causes for such symptoms should be excluded by means of appropriate investigations. Investigations may include imaging such as high resolution computer tomography (HRCT), bronchoalveolar lavage (BAL), and biopsy as clinically indicated (see also Table 7: refer to dose adjustment table for interstitial lung disease/pneumonitis).

Dose Modification and Management — Interstitial Lung Disease/Pneumonitis

| ose mounication and managem | ent interstitut Eung Disease/I neumonitis |
|--------------------------------------------------------------------------------------------------------------------------------------|--------------------------------------------------------------------------------------|
| CTCAE Grade | Abemaciclib Dose Modifications |
| Grade 1 or 2 | No dose modification is required. |
| Persistent or recurrent Grade 2 toxicity that does not resolve with maximal supportive measures within 7 days to baseline or Grade 1 | Hold dose until toxicity resolves to baseline or Grade 1. Resume at next lower dose. |
| Grade 3 or 4 | Discontinue abemaciclib. |

Dose Modification and Management — Nonhematologic Toxicities Excluding Diarrhea, ALT Increased, and ILD/Pneumonitis

| CTCAE Grade | Abemaciclib Dose Modifications |
|---------------------------------------------------------------------------------------------------------------------------------------------------|---------------------------------------------------------------------------------------|
| Grade 1 or 2 | No dose modification is required. |

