| | | | | ticlopidine | diphenhydrami | | diltiazem |
| | | | | topiramate | ne | | cimetidine |
| | | | | | doxepin | | amiodarone |
| | | | | | doxorubicin | | NOT |
| | | | | | escitalopram | | azithromycin |
| | | | | | halofantrine | | chloramphenic |
| | | | | | histamine H1 | | lo |
| | | | | | receptor | | ciprofloxacin |
| | | | | | antagonists | | delaviridine |
| | | | | | hydroxyzine | | diethyl- |
| | | | | | levomepromazi | | dithiocarbamat |
| | | | | | ne | | ပ |
| | | | | | methadone | | fluvoxamine |
| | | | | | metoclopramid | | gestodene |
| | | | | | o | | imatinib |
| | | | | | mibefradil | | mibefradil |
| | | | | | midodrine | | mifepristone |
| | | | | | moclobemide | | norfloxacin |
| | | | | | perphenazine | | norfluoxetine |
| | | | | | ranitidine | | star fruit |
| | | | | | red-haloperidol | | voriconazole |

Page 64 of 71

| ritonavir | ticlopidine | tripelennamine |
|-----------|-------------|----------------|
| | | |
| | | |
| | | |
| | | |
| | | |

| | | 3A4,5,7 | HIV Antivirals: | efavirenz | nevirapine | barbiturates | carbamazepine | efavirenz | glucocorticoids | modafinil | nevirapine | oxcarbazepine | phenobarbital | phenytoin | pioglitazone | rifabutin | rifampin | St. John's wort | troglitazone |
|-------------------------------|----------|------------------|-----------------|-----------------|-------------------|---------------|--------------------|-----------|-----------------|---------------------|------------|---------------|---------------|-----------|--------------|-----------|----------|-----------------|--------------|
| | | (7) | HIV | о — | u U | ba | carb | o o | gluc | ш |)U | oxc | bhe | ld | pic |  | . | St. J | tro |
| | | 2E1 | ethanol | isoniazid | | | | | | | | | | | | | | | |
| ticlopidine tripelennamine | | $\frac{2D6}{}$ | dexamethasone | rifampin | | | | | | | | | | | | | | | |
| | INDUCERS | 2C19 | carbamazepine | norethindrone | NOT | pentobarbital | prednisone | rifampin | | | | | | | | | | | |
| | II | $\frac{2C9}{}$ | rifampin | secobarbital | | | | | | | | | | | | | | | |
| | | 2C8 | rifampin | | | | | | | | | | | | | | | | |
| | | $\overline{2B6}$ | phenobarbital | rifampin | | | | | | | | | | | | | | | |
| | | 1A2 | broccoli | brussel sprouts | char-grilled meat | insulin | methylcholanthrene | modafinil | nafcillin | beta-naphthoflavone | omeprazole | tobacco | | | | | | | |

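### The ban on all CYP3A inducers, read with Appendix A, reaches the corticosteroids that the pneumonitis guidance allows, and no section reconciles the two

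*Combined protocol and SAP*

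**What the plan says.** Four places in the protocol bear on this.

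- **Section 7.3.7 (restrictions on concomitant therapies)** closes with: "For the purpose of this study, all CYP3A inducers will not be permitted on this study; please see Appendix A". The same sentence tells sites to "refer to crediblemeds.org for a more comprehensive list of prohibited medications". If the website is the fuller list of prohibited drugs, Appendix A is itself being used as a prohibited list. The sentence stands under a sub-heading that names strong inducers only.
- **Appendix A, inducers table**, reads in the relevant entry: "3A4,5,7 | HIV Antivirals: | efavirenz | nevirapine | barbiturates | carbamazepine | efavirenz | glucocorticoids". Glucocorticoids appear as a class, with no dose, route, duration or strength attached.
- **Section 7.4.5 (ILD/pneumonitis)** says of new or worsening pulmonary symptoms: "these symptoms should be investigated and treated as per local clinical practice and/or guidelines (including corticosteroids as appropriate"). Its table gives, for Grade 1 or 2, "No dose modification is required"; for persistent or recurrent Grade 2, "Hold dose until toxicity resolves to baseline or Grade 1. Resume at next lower dose"; and for Grade 3 or 4, discontinuation.
- **Section 7.4.6 (general guidance for concomitant therapy)** asks that CYP3A inducers be avoided and alternatives considered. It contains no prohibition and does not mention corticosteroids.

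**The concern.** One section forbids a class of drug during the study, and another names the same class as treatment for an adverse reaction. Section 7.4.5 describes ILD/pneumonitis as an identified reaction to abemaciclib, mostly Grade 1 or 2, with serious and fatal cases reported. A site treating such a participant should not have to work out which section prevails. Different sites or investigators could also resolve the conflict differently. The same participant could then be recorded as correctly managed under 7.4.5 or as a deviation under 7.3.7.

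Interpretation is a secondary issue. Section 7.3.7 gives reduced activity as the reason for restricting inducers. If corticosteroids are given during treatment, a reader of the results will want to know who received them.

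**Working it through.** No sample size, power or error rate is involved, so there is nothing to recompute. The check sets the texts side by side.

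**Step 1. Does the ban cover glucocorticoids?** Read literally, yes. Section 7.3.7 says *all* inducers and refers to Appendix A, and Appendix A lists glucocorticoids under 3A4,5,7. The table is rotated and damaged in extraction, but the column label and the entry fall in the same run of text, so the reading is secure. The one textual ground for a narrower ban is the sub-heading naming strong inducers, which disagrees with the word *all* beneath it. Appendix A does not grade inducers by strength, so it cannot settle that disagreement.

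**Step 2. Can corticosteroid treatment under 7.4.5 coincide with dosing?** This depends on grade.

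| ILD/pneumonitis grade | Abemaciclib under 7.4.5 | Overlap with a corticosteroid |
|---|---|---|
| 1 or 2 | Continues unchanged | Yes, if one is judged appropriate |
| Persistent or recurrent 2 | Held, then resumed one level lower | Possible before the hold, and after resumption if the course is still running |
| 3 or 4 | Discontinued | Largely none, if the ban means concomitant use |

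The hold in the second row applies only when maximal supportive measures have not resolved the event within 7 days. The table therefore expects supportive treatment to begin while dosing continues.

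**Step 3. Is there an exemption?** None was found in 7.3.7, 7.4.5, 7.4.6 or Appendix A. Section 7.4.6 does not supply one. Its softer wording adds a second inconsistency, because the same drugs are not permitted in one section and only to be avoided in another.

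**Step 4. Can the size of any exposure effect be stated?** No. Section 7.3.7 gives a 67% fall in active exposure with rifampin, a strong inducer, and calls the effect of moderate inducers unknown. It gives no figure for glucocorticoids.

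**The case against.** The strongest reply is that the conflict is narrow. Corticosteroids are conditional in 7.4.5, left to local practice and used only where appropriate. The drug is stopped at Grade 3 or 4 and held for persistent or recurrent Grade 2. Stating that a dose change is not required at Grade 1 or 2 does not forbid a hold. Section 7.4.6 shows that avoidance may be all that was meant. Pneumonitis is also absent from the protocol's table of reactions seen in at least 10% of patients on 200 mg twice daily monotherapy. If that breast cancer experience carried over (an assumption), fewer than 10 × 0.10 = 1 case would be expected among 10 participants.

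Most of this stands, and it limits the point. It does not remove it: the texts still disagree at Grade 1 or 2 and on resumption, and no wording says which governs.

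A reader might infer more than the documents support:

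- **That a site can never follow both sections.** The conflict arises only when a corticosteroid is judged appropriate during dosing.
- **That treated participants would be withdrawn and their data lost.** The criterion in Section 3.4 is discretionary: "Significant participant or protocol noncompliance that, in the opinion of the Principal Investigator, warrants withdrawal of treatment". Its examples are not taking study medication and missing visits. Section 8.2 defines no per-protocol set that drops participants for a deviation. Section 8.2.3 counts treated participants without a response assessment as non-responders, and Section 3.4 asks that withdrawn participants complete follow-up.
- **That each case costs 10 points of response rate.** One participant in 10 is 10 percentage points, but taking a corticosteroid neither removes a participant nor reverses a response. The documents give no rate of corticosteroid use from which to count cases.

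**Conclusion.** The contradiction is real and present in the current text. Section 7.3.7 with Appendix A excludes glucocorticoids as CYP3A inducers, Section 7.4.5 allows for them as pneumonitis treatment, and Section 7.4.6 states a weaker restriction on the same drugs. It applies where abemaciclib continues at Grade 1 or 2, or is resumed after a hold while a corticosteroid is still being given. It largely disappears at Grade 3 or 4.

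This rests on two readings: that Appendix A functions as a prohibited list, which the wording of 7.3.7 supports, and that *all* prevails over the narrower sub-heading. If the sub-heading were meant to prevail, the text would still need correcting to say so.

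No effect on response rate or exposure is claimed. A reader might be tempted to apply the 67% figure to corticosteroids, but it belongs to a strong inducer and does not measure their effect. The point merits correction because the reaction can be fatal and the repair is cheap.

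**What to change.** The sponsor should reconcile four places: Section 7.3.7 (including its strong-inducer sub-heading against the word *all*), Section 7.4.5, Section 7.4.6 and the 3A4,5,7 inducer entry in Appendix A. Together they should state consistently whether the inducer restriction covers glucocorticoids given for ILD/pneumonitis, and whether inducers are prohibited or to be avoided. Which rule is clinically right is for the sponsor, and none is proposed here.

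On the analysis side, systemic corticosteroid use during treatment can be identified within the concomitant-medication summary by therapeutic class already planned in Section 8.5.2. Section 12.1 leaves medications given for procedures out of data collection, so those would not be captured.

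The cost is amendment wording in four places and one line in a planned summary, with no new data collection.
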